ACE, Resilience, and Substance Use Disorder: Maternal and Baby Outcomes in the First Year of Life

Investigator: [name], MD

Co-Investigators: [name], [name], [name], MS, PhD, MBA, [name], MA

2/19/2020

1. Objective/ Purpose

The purpose of this study is to understand the maternal factors that contribute to the health of an infant born to a mother with substance use disorder (SUD). We will evaluate whether or not the outcomes of maternal and baby health can be identified early through maternal screening tools, including the Adverse Childhood Experience (ACE) questionnaire and the 7Cs Resiliency Tool.

2. Hypothesis

Mothers with SUDs that have higher maternal ACE scores will have children with poor outcomes, including difficulty reaching developmental milestones, poorer adherence to vaccination schedule guidelines, and more frequent ER visits in the first year of life. However, high maternal resilience scores may counter the high ACE scores and allow for improvement of poor health outcomes in these populations.

3. Background

Adverse Childhood Experiences (ACEs) are traumatic or life-threatening events that occurred to an individual during the ages 0-17 and are measured with the ACE Score questionnaire. These experiences include being a victim of physical and sexual abuse, neglect, and exposure to household dysfunction such as parental substance abuse or incarceration¹. Multiple studies have shown that the number of ACEs an individual experiences correlates with his or her risk in developing chronic health issues such as diabetes, asthma, and hypertension later in life²⁻⁴. In addition, ACEs correlate with a higher risk of engaging in risky behaviors such as substance use⁵.

A recent survey conducted by the Substance Abuse and Mental Health Services Administration (SAMHSA) showed that 5.4% of pregnant mothers had used illicit drugs including marijuana, opioids, and cocaine in the past month⁶. Moreover, ACE scores of pregnant women have been linked to poor coping mechanisms such as illicit drug use during pregnancy⁷. These scores also impact prenatal,

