perinatal, and post-natal health⁸. For example, babies who were exposed to opioids in utero had significant associations with poorer health outcomes and delays in developmental stages⁹. Another study concluded that mothers suffering from substance use disorder engage in poor parenting practices such as “limited or absent parental monitoring and lower levels of parental involvement.”¹⁰ Currently, many medical practices are using ACE scores as a general screening tool to help identify health risks and provide individualized care and family support¹¹. Recent studies show that identifying positive childhood experiences is important when evaluating the impact of ACEs. Protective factors, such as resilience, can offset the negative health impacts of trauma^{12,13}. Described as good outcomes in the face of a threat to wellbeing¹³, resilience can be quantified by using a questionnaire called the 7Cs tool¹⁴. The 7Cs tool, which examines an individual’s competence, confidence, character, connection, contribution, coping and control, is a valid method to measure resilience. Currently, the 7Cs tool is internally validated for adolescents that have experienced trauma, and it has shown a correlation between better outcomes with a higher resilience score despite having higher ACE scores. Overall, there is limited information regarding ways to identify and determine the health impact of maternal resilience. More research is necessary to understand how ACEs and resilience affect postpartum outcomes in mothers with SUD and their child.

Significance of the Research

Currently, little research has been conducted to study the relationship between ACEs and maternal resilience and the health outcomes of mothers with SUDs and their newborn baby. Understanding factors that show a strong correlation with maternal and fetal health outcomes would allow health care providers to identify risks earlier, offer prenatal interventional care, and provide tailored resources for mothers and their infant.

4. Study Design

This is a prospective observational study that will require the initial administration of both the ACEs questionnaire and 7Cs resilience tool, followed by one year of chart reviews and/or phone calls to follow-up with patients regarding the identified outcome measures.

5. Proposed research Plan

A. Subjects

Number of subjects: 100

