questionnaire and 7C Resilience Tool. After giving birth, patient charts will be monitored for maternal commitment to treatment, child custody status, the number of times the child was admitted to the emergency room, adherence to recommended pediatric vaccination schedules, and infant developmental milestones. These measurements will be taken over the course of 1 year after child birth.

Summary of visit procedures: Pregnant mothers will meet with any of the co-investigators prenatally to complete the ACE questionnaire and 7C Resilience Tool. After the initial intake, outcome measures will be collected via chart review or verbally through phone call with the mother. Data will be collected at birth, 2 months, 4 months, 6 months, and 1 year after birth.

Procedures just for research purposes: The ACEs questionnaire and 7C Resilience Tool are not included in standard prenatal care and are solely being administered for research purposes. If the subjects were not enrolled in this study, the only difference in care would be the absence of either screening tool being administered prenatally.

How participation differs from standard of care/ study duration: As an observational study, participating subjects will be provided the appropriate standard-of-care.

Study Duration: Pregnant mothers will be enrolled between March 1, 2020 to August 1, 2020. All mothers will be followed for one year postpartum. The total duration of the project for the individual will be the duration of the pregnancy as well as the child's first year of life. This study will be conducted between March 1, 2020 - January 31, 2020.

Data Analysis Plan, Statistical Tests, and Sample Size Rationale

Outcome measures being followed at birth of baby, and at 2, 4, 6 and 12 months after birth:

1. Is the mother still parenting and have custody of the baby?
2. Is the mother receiving treatment for substance use disorder?
3. Has the baby reached expected developmental and health milestones after delivery?
4. How many Emergency Room visits did the baby have postnatally?
5. Does the child meet vaccination schedule as proposed by the CDC?

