Sample size. The key outcomes of the study will include binary measurements (parenting, custody, continued treatment, etc.) measured at 2, 4, 6 and 12 months after birth. These outcomes will be related to the pre-natal scores of the ACE and 7C survey tools. Based on a repeated measures design, a sample size of 100 will provide >90% power to detect an odds ratio of 2 or greater for each standard deviation above the mean of the ACE scale (1-10) assuming a mean of 3.7 and a standard deviation of 2.7 and a response proportion of 0.50.

Data Analysis. The checking, assessment and analysis of the data will be carried out in a blinded fashion. Demographic and clinical characteristics will be presented using means with standard deviation for continuous variables and counts with proportions for categorical variables. The statistical analysis will be carried out using “intention-to treat” and “per-protocol” approaches. The primary outcomes (parenting, custody, continued treatment, etc.) will be analyzed using generalized estimating equations (GEE) appropriate for repeated measures over time. Odds ratios with 95% confidence intervals for the relationships of ACE and 7C with the clinical outcomes will be presented.

6. Risks and benefits

- A. Potential Risks due to Study Participation: No study treatments will be included in this observational study. However, in some cases, re-traumatization is a possibility and necessary resources will be made available to the subject.
- B. Minimizing Risks: Risks to subjects will be minimized by the study design, which is observational and not anticipated to be risky towards the mother or fetus. Subjects being seen at the Addiction Medicine clinic and Labor and Delivery Ward will have normal access to treatment and follow-up visits, which follows normal standard of care at Cooper Hospital.
- C. Potential Benefits: Potential benefits of this study would be increased adherence to substance use disorder (SUD) treatment, appropriate follow-up with pediatricians per recommended vaccination schedule, and identifying risk factors during pregnancy to initiate early intervention practices. Society may benefit from this research by understanding the risks of ACEs and resilience scores of pregnant mothers suffering from SUD and how it affects the care of their newborn child. The findings of this

study may benefit the resources and management of mothers with SUD during pregnancy and postpartum.

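### The hypothesis that resilience counters high ACE scores has no matching analysis: joint entry of ACE and 7C is not stated, and no ACE × 7C term is named

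*Combined protocol and SAP*

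**What the plan says.** Section 2 (Hypothesis) first predicts worse child outcomes with higher maternal ACE scores, then adds: "However, high maternal resilience scores may counter the high ACE scores and allow for improvement of poor health outcomes in these populations". Section 3 (Background) supports this with two statements that point in different directions. One is that "Protective factors, such as resilience, can offset the negative health impacts of trauma". The other says of the 7Cs tool that "it has shown a correlation between better outcomes with a higher resilience score despite having higher ACE scores".

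In section 5.B, the Sample size paragraph says: "These outcomes will be related to the pre-natal scores of the ACE and 7C survey tools". Its power statement concerns ACE alone: 100 mothers, an odds ratio of 2 per standard deviation, response proportion 0.50, power above 90%. The Data Analysis paragraph names generalized estimating equations (GEE) for the primary outcomes and then promises: "Odds ratios with 95% confidence intervals for the relationships of ACE and 7C with the clinical outcomes will be presented". Nothing in the document says whether ACE and 7C share a model, and no product term or ACE odds ratio by level of 7C is named.

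One child outcome in the hypothesis is "more frequent ER visits in the first year of life". The outcome list collects it as a number: "How many Emergency Room visits did the baby have postnatally".

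**The concern.** *Counter* can mean two things, and they need different analyses.

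- **Additive benefit.** Mothers with higher 7C do better at any given ACE score. This needs the 7C odds ratio adjusted for ACE, so both scores must be in one model.
- **Buffering.** The ACE effect is weaker when 7C is high. This needs an ACE × 7C term or an equivalent. A GEE without one forces the same ACE odds ratio at every level of 7C.

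The text secures neither. At stake is the interpretation of the resilience half of the hypothesis. A protective 7C odds ratio could be reported as resilience countering ACEs although the analysis cannot show that the ACE effect was any weaker. An interaction added after the data were seen would be post hoc. Emergency room visits add a smaller gap: they are a count, and odds ratios are the only effect measure the plan names.

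**Working it through.** **Inputs from the protocol (section 5.B, Sample size):** n = 100; ACE odds ratio 2 per SD (ln 2 = 0.693); response proportion 0.50; ACE mean 3.7, SD 2.7, scale 1–10; four visits after birth (2, 4, 6 and 12 months).

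**Assumptions (not in the protocol):** two-sided 5% level; the size of any interaction; within-mother correlation 0.3–0.7; ACE–7C correlation 0 or −0.3 (−0.1 to −0.5 in step 2); complete visits.

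**1. The plan's own figure.** For logistic regression on a standardised covariate, power = Φ(√(n·p(1−p))·ln OR − 1.960).
- One measurement: √(100 × 0.25) × 0.693 − 1.960 = 3.466 − 1.960 = 1.506, so power is 93.4%.
- Sample size for 90%: (1.960 + 1.282)² / (0.25 × 0.693²) = 87.5, so 88 mothers.
- Four visits at within-mother correlation 0.5: the design factor is (1 + 3 × 0.5)/4 = 0.625, the effective n is 160, and power is 99.2%.

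The stated figure reproduces for the ACE main effect. It assumes no interaction.

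**2. Additive reading: 7C not adjusted for ACE.** Suppose 7C has no effect at a given ACE score and the two scores correlate at −0.3. The 7C slope picks up about 0.693 × (−0.3) = −0.208 on the log-odds scale, an odds ratio of 0.81. Averaging over the remaining ACE variation pulls this to 0.83. At correlations of −0.1 and −0.5 the result is 0.94 and 0.73. With both scores in the model it is 1.00.

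**3. Buffering reading: main effects only.** Take uncorrelated standardised scores, ACE odds ratio 2 at mean 7C, and no 7C effect at ACE −1 SD, which is score 1 because (1 − 3.7)/2.7 = −1.00. The 7C slope is then zero at −1 SD, so the 7C odds ratio at mean ACE equals the interaction odds ratio. The true ACE odds ratio is 2 divided by the interaction odds ratio at 7C −1 SD, and 2 multiplied by it at 7C +1 SD. The last two columns are large-sample fits without a product term.

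| Interaction OR | True ACE OR at 7C −1 SD / +1 SD | Fitted ACE OR | Fitted 7C OR |
|---|---|---|---|
| 0.50 | 4.0 / 1.0 | 1.8 | 0.55 |
| 0.67 | 3.0 / 1.3 | 1.9 | 0.68–0.69 |
| 0.80 | 2.5 / 1.6 | 2.0 | 0.80 |

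In the first row ACE has no effect at high 7C and a fourfold odds ratio at low 7C, yet the fit reports one ACE odds ratio of 1.8. Additive data built with odds ratios 1.8 and 0.55 and no interaction give the same main-effects table.

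**4. What a product term would show.** GEE simulation: n = 100, four visits, within-mother correlation 0.5, uncorrelated scores, bias-corrected robust SE, 2,000 runs per scenario.
- Interaction OR 0.50: the main-effects 7C OR is 0.55 under buffering and 0.55 under the matched additive data. The product term is 0.49 against 0.99, significant in 83% against 4% of runs.
- Interaction OR 0.67: the 7C OR is 0.68 against 0.68. The product term is 0.66 against 1.00, significant in only 44% under buffering (median 95% CI 0.43–1.03).

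Over the assumed correlations, interaction power is 71–94% at OR 0.50, 34–61% at 0.67 and 13–23% at 0.80. Missing visits would lower these figures.

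**The case against.** **The plan is silent, not contradictory.** Its wording is compatible with one GEE holding both scores, and this short protocol lists no covariates at all. That stands. A reader might infer that the sponsor intends an unadjusted 7C analysis; the document does not say so. The 0.83 shows what happens if 7C is left unadjusted.

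**The hypothesis may not need an interaction.** The resilience sentence is tentative, and one Background statement is additive in sense. On that reading a joint main-effects model is enough. This stands too, but joint entry is not stated, and the other Background statement speaks of offsetting harm. The sponsor should say which is meant.

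**The matched comparison was built to match.** A reader might infer that the 7C odds ratio would be the same whether or not buffering exists. The check does not support that. It shows that an additive truth giving the same value exists, so the value alone cannot decide, and 0.55 depends on assuming no 7C effect at ACE −1 SD.

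**Unplanned interactions and false positives.** A reader might put a number on post hoc testing across the five listed outcomes: 1 − 0.95⁵ = 23%. That is an illustration for independent tests only. The outcomes come from the same mother–infant pairs and are probably correlated, which would lower it, and the plan proposes no selective interaction testing.

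**Limited yield at n = 100.** This is correct. Power starting at 71% for a large interaction is not reliable detection. It is a reason for exploratory status and interpretation by interval, not for leaving the question without an analysis.

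**Emergency room visits are a separate matter.** In part: the plan ties GEE to its primary outcomes, illustrated by binary ones, and never says that visit counts will be reported as odds ratios. But it names no other measure for an outcome in the hypothesis.

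**Conclusion.** The point holds as a cheap improvement. As written, the plan does not secure an answer to the resilience hypothesis under either meaning of *counter*. The additive meaning needs joint entry, which is not stated. The buffering meaning needs a term that is not named, and main-effect odds ratios cannot supply it.

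That main effects cannot identify moderation needs no assumed inputs. The sizes do: 0.83 rests on an ACE–7C correlation of −0.3 and the plan's ACE odds ratio of 2; 0.55 rests on an interaction odds ratio of 0.50 with no 7C effect at ACE −1 SD; the power ranges rest on the assumed correlations and complete visits.

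A reader might also infer that the sample size is wrong. It is not: the figure above 90% reproduces for the ACE main effect. It simply does not extend to the interaction.

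**What to change.** Amend the Data Analysis and Sample size paragraphs as follows.

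1. State whether *counter* means an additive benefit, buffering, or both.
2. Enter standardised ACE and 7C together in the GEE for each binary outcome, and report the 7C odds ratio adjusted for ACE.
3. Add the ACE × 7C product as a prespecified exploratory analysis with a small-sample-corrected robust standard error. For every outcome, report the interaction odds ratio with its 95% confidence interval, and the ACE odds ratio at 7C −1 SD, mean and +1 SD. Interpret the intervals; do not select significant results.
4. Analyse emergency room visits with a count model that allows overdispersion, using the same terms and reporting rate ratios.
5. State that the power above 90% covers the ACE main effect with no interaction assumed. State also that interaction precision is limited: roughly 70–95% power at odds ratio 0.50, 35–60% at 0.67 and 13–23% at 0.80 under the correlations assumed here, to be replaced by the sponsor's own inputs. A null interaction therefore does not rule out buffering.

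The cost is a few sentences, one extra term per outcome and one count model, with no new data, visits or participants. The downside is a little more analysis and an openly stated limit on precision for the resilience question.
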